Among patients living with HIV infection, cardiovascular disease (CVD) is increasingly prevalent and has become a significant cause of mortality. Identifying the mechanisms that are distinctive to the atherosclerotic disease process in HIV-infected patients is crucial to develop appropriate strategies to treat and prevent CVD in this patient population. Activation of the innate immune system may stimulate inflammatory mechanisms of atherosclerosis development. Loss of gastrointestinal (GI) mucosal epithelial integrity and loss of CD4+ T-lymphocytes in the intestinal lamina propria occur in HIV-infected patients. Translocation of microbial products from the intestinal lumen into the systemic circulation has been demonstrated to be increased in HIV-infected patients and we hypothesize to be a key driver of monocyte and macrophage activation. In turn, these pro-inflammatory monocytes and macrophages can induce atherosclerotic disease development. However, the respective roles of microbial translocation and the gut mucosal immunity on cardiovascular inflammation in HIV infection are not yet known. Furthermore, no treatment strategy as yet exists to effectively target proatherogenic immune activation as an important mechanism of CVD in HIV-infected patients.

Our central hypothesis is that increased microbial translocation from impaired epithelial integrity and impaired mucosal immunity activates the innate immune system, causing proatherogenic monocyte and macrophage activation and atherosclerotic disease development in HIV disease. Furthermore, we hypothesize that intervening to enhance the intestinal epithelial barrier using a glucagon-like peptide 2 (GLP-2) analog will decrease intestinal permeability to microbial products and thus ameliorate monocyte/macrophage pathways that lead to downstream decrease in arterial macrophage activity, inflammation and atherosclerotic disease risk. *We will test our hypotheses in studies proposed in the following specific aims:*

Aim 1: To determine the role of innate immune system activation in atherosclerosis development among HIV-infected patients, focusing on microbial translocation from impaired GI mucosal barrier as the hypothesized inciting event for activation of monocytes and macrophages.

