Overview of the Approach: A total of 90 subjects (70 subjects with chronic HIV-1 infection and 20 HIVnegative control subjects) will be recruited (See Figure 2). For the neurological substudy, an additional 15 HIV-negative control subjects will be recruited and complete Visit A and Visit B (see Figure 1b, not shown in Figure 2 flowchart). Ninety subjects will complete **Baseline Study Part 1** of the cross-sectional study. **Baseline Study Part 2** will be performed in a subset of 60 HIV-infected patients and 10 HIVnegative controls. The 60 HIV-positive patients who complete Baseline Studies Part 1 and Part 2 will enter the **Randomized Study of Teduglutide vs. Placebo**. The tests and procedures obtained during the Baseline Studies Part 1 and Part 2 for these 60 HIV-positive participants will serve as the baseline measurements for the randomized study (they are not repeated) in order to minimize risk from exposure to study procedures for the participants and to maximally utilize the study data.

Having the control group will help us establish whether assessed relationships between GI epithelial integrity, microbial translocation, immune activation, and cardiovascular imaging markers are HIV-specific. Adding the neurological substudy control group (n=15) will help us potentially identify a HIV-

specific, cardiovascular and inflammatory link to cognitive impairment and depression. The control group can also serve as a comparison group with which to compare the HIV patients.

Figure 2

After all subjects have completed the study, transcriptomic profiling by RNA-Seq will be performed in 7 HIV+ participants with greatest degree of coronary disease seen on CTA vs. 7 HIV+ participants without and 7 HIV+ participants with the greatest degree of bacterial translocation vs. 7 HIV+ participants with the least amount of microbial translocation.

Participants will be recruited from the Boston area from infectious disease clinics, HIV community centers and also via IRB-approved advertisements. Patients will also be recruited via referral by primary care providers, infectious disease providers, newspaper advertisement, posted flyers, and Partners subject recruitment broadcast. After obtaining informed consent, baseline measurements and studies will be performed.

Inclusion criteria for HIV-infected participants:

- 1. Men and women age 21-65 with previously diagnosed HIV disease

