The Baseline Study Part 1 includes 10 patients with HIV and 10 patients without HIV and does not involve a colonoscopy, CT scan, or PET scan. Some of the exclusion criteria listed above are only relevant for participants undergoing a colonoscopy, CT scan, or PET scan. Patients participating only in the Baseline Study Part 1 will be excluded based on the following criteria only:

- 1. History of clinically significant gastrointestinal disease including but not limited to: colon cancer, intestinal obstruction, ulcerative colitis, Crohn's disease, or history of C. difficile within the past 3 months
- 2. First-degree relative with history of colon cancer
- 3. Active gall bladder, biliary or pancreatic disease
- 4. Female subject who is pregnant, nursing or less than 8 weeks post partum.
- 5. Use of any immunomodulatory agents within 30 days prior to study enrollment
- 6. Renal disease or creatinine >1.5 mg/dL (contrast will be administered during CT angiography of the heart)
- 7. History of myocardial infarction, decompensated cirrhosis, or any other condition that in the opinion of the investigator will compromise ability to participate in the study
- 8. Currently taking anticoagulants including but not limited to: heparin (Hep-Lock, Hep-Pak), Hep-Pak CVC, Heparin Lock Flush), warfarin (Coumadin), tinzaparin (Innohep), enoxaparin (Lovenox), danaparoid (Orgaran), dalteparin (Fragmin), clopidogrel (Plavix)
- 9. Subject taking any of the following medications: systemic steroids (inhaled or nasal steroid therapy is permitted), interleukins, systemic interferons (e.g. local injection of interferon alpha for treatment of HPV is permitted), systemic chemotherapy including oral chemotherapeutic agents, methotrexate, octreotide, growth hormone, antiarrhythmics including digoxin, antiepileptics, immunosuppressants, vancomycin, rifampin, aminoglycosides, clonidine, prazosin, lithium and ritonavir-boosted lopinavir (Kaletra).
- 10. Subjects receiving high dose statin therapy (a stable low or moderate dose of statin is permitted)
- 11. Initiation of statin therapy or change in statin dose <90 days prior to entry
- 12. Body weight greater than 350 lbs
- 13. Active illicit drug use
- 14. History of malignancy in the last 5 years, with the exception of surgically cured non-metastatic non-melanoma skin cancers

- 15. Prior recipient of a HIV vaccine
- 16. Currently receiving pre-exposure prophylaxis (PrEP)

IV. Subject Enrollment

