*Multivariate modeling:* For outcomes TBR and plaque, to control for potential confounders, multivariate linear regression modeling will be used to identify factors independently associated with increasing TBR and increasing number of atherosclerotic plaque lesions. Similar methods will be applied for neurocognitive score and mood assessment to cerebral FDG-PET/CT. Model variable selection will be based on "change-in-estimate" method⁵⁸. Candidate covariates to be chosen for entry into our model include all covariates significant on individual univariate models (p<0.05), potential confounders, and biologically plausible covariates with established relationships to atherosclerosis. Colinearity among covariates will be identified and redundant covariates will be excluded from the model. Confounders will be identified by observing changes in effect estimate β ; colinearity will be identified by observing changes in effect estimate β ; as well as by using Variance Inflation Factor criterion. Regression diagnostics will be used to check if model assumptions are met⁵⁸. We will control for age, gender, race, smoking, lipids, diabetes mellitus, WRAT 4 reading versus educational years, and hypertension in addition to other potential confounders identified by methods above.

Between group comparisons: We will also assess differences in microbial translocation, mucosal immunity and GI permeability markers among those with coronary atherosclerosis vs. those without atherosclerosis and in those with elevated TBR (>1.8) vs. those without elevated TBR. 2 group comparisons will be performed using Student's T-test if the outcome variable is normally distributed. Distributions will be tested for normality using the Wilk-Shapiro test and examination of the histogram distributions. If the outcome variable is not normally distributed, we will consider appropriate transformation to approximate a normal distribution. Alternatively, if distributions are non-normal despite the applied transformation, we will use nonparametric Wilcoxon rank sum test to compare the 2 groups. All tests will be 2-sided, and a p < 0.05 will be considered statistically significant.

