Sample Size Determination: With 70 HIV-infected patients and 20 uninfected controls, we can detect a bivariate correlation Pearson's coefficients of at least 0.58, 0.33, and 0.29 can be detected at a 5% significance level with 80% power within uninfected, infected, and both the uninfected and infected subjects respectively. The detectable effect sizes of markers between elevated - and without elevated TBR groups will depend on the distribution of the observed TBR and the markers' distributions. If the rate of elevated TBR is 50% among the whole cohort of 70 patients, then an effect size with Cohen's effect size d>0.68 can be detected by a two-sided independent samples t-test at a 5% significance level with 80% power.

RNA Sequencing Subset (Aim 1B):

Statistical Analysis Plan: The BioConductor package LIMMA will be used to identify genes which are differentially expressed between the two compartments. Holm's and Benjamin-Hochberg methods will be applied for correcting multiple testing. *Sample Size Determination*: For *RNA-Seq* analysis using 7 patients with CVD and 7 without, there will be 27,000 genes to be included in the initial testing of which about 140 genes are expected to be differentially expressed significantly with a two to three times of the standard deviation of the fold difference in the expression levels. With a targeted false discovery rate (FDR) of 20% or less, the power to detect at least 112 differentially expressed genes significantly with an effect size of 2.7×SD with p<0.0011 (i.e., multiple testing adjusted alpha=0.0011) will be at least 80%.

Randomized Study of Teduglutide vs. Placebo (Aim 2):

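### The elevated-TBR comparison in Aim 1A is sized on 70 people, but only 60 HIV-infected participants have a TBR, and the plan does not say whether HIV-negative controls enter the unadjusted test

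*Combined protocol and SAP*

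**What the plan says.** Aim 1 (Specific Aims) is posed within HIV infection: "To determine the role of innate immune system activation in atherosclerosis development among HIV-infected patients". The univariate analysis in the Aim 1A Statistical Analysis Plan is likewise limited to HIV-infected patients.

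The paragraph on between-group comparisons then adds two contrasts of translocation, mucosal-immunity and permeability markers: people with coronary atherosclerosis against those without, and "in those with elevated TBR (>1.8) vs. those without elevated TBR". It specifies a t-test, or a Wilcoxon rank sum test if normality fails. It names no HIV restriction, stratification or adjustment.

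The Aim 1A Sample Size Determination opens with the correlations, "With 70 HIV-infected patients and 20 uninfected controls". For the TBR groups it continues: "If the rate of elevated TBR is 50% among the whole cohort of 70 patients", then "Cohen's effect size d>0.68 can be detected by a two-sided independent samples t-test" "at a 5% significance level with 80% power". It has no sample-size statement for plaque versus no plaque.

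On who is imaged, Subject Selection says that Baseline Study Part 2 "will be performed in a subset of 60 HIV-infected patients and 10 HIVnegative controls". The eligibility text for people taking part only in Baseline Study Part 1 says that this part "includes 10 patients with HIV and 10 patients without HIV and does not involve a colonoscopy, CT scan, or PET scan".

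**The concern.** A TBR comparison needs people with a TBR. The parent study has 60 HIV-infected people and 10 controls with one, and the other 10 HIV-infected participants have no PET. No set of 70 HIV-infected people can be split by TBR, so the sizing figure cannot describe the within-HIV question that Aim 1 asks.

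If the 70 is the imaged group of 60 plus 10, a second issue follows. The background section says that LPS and sCD14 are raised in chronic HIV infection, and it argues that arterial disease is too. If both hold in this sample, controls would gather in the low-TBR or no-plaque group and bring lower marker values with them. An unadjusted test could then show a marker difference that restates HIV-infected versus uninfected, and it could be taken as evidence for the translocation-to-atherosclerosis link within HIV.

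**Working it through.** **Inputs from the documents.** Two-sided t-test, alpha 0.05, power 80%, d = 0.68, 70 people split 50/50 (Aim 1A sample size); 60 HIV-infected and 10 controls imaged (Subject Selection); TBR cut 1.8 (between-group comparisons); TBR mean 2.24, SD 0.35 in a similar patient population (Aim 2 sample size).

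**Assumed, not in the documents.** The marker gap between HIV-infected people and controls (0.5 to 1.0 SD), and the share of controls with elevated TBR.

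**1. The plan's figure.** For group sizes n1 and n2, power is the probability that a noncentral t with n1 + n2 − 2 degrees of freedom and noncentrality d·√(n1·n2/(n1+n2)) exceeds the two-sided 5% critical value.
- 35 vs 35: √(35·35/70) = 4.183, and 0.68 × 4.183 = 2.845. Power is 80.1%; detectable d at 80% power is 0.679. The stated 0.68 reproduces.

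**2. The within-HIV question at the same 50% rate.**
- 30 vs 30: √(30·30/60) = 3.873, and 0.68 × 3.873 = 2.634. Power is 73.6%; detectable d is 0.736.

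**3. The split implied by the plan's own TBR figures.** Assume TBR is normal and that 2.24 (SD 0.35) is on the same scale as the 1.8 cut. Then (1.8 − 2.24)/0.35 = −1.257, so 89.6% lie above 1.8, and 60 × 0.896 = 53.7.
- 54 vs 6: √(54·6/60) = 2.324, and 0.68 × 2.324 = 1.580. Power is about 34%; detectable d is about 1.23.

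**4. Possible bias if the 10 controls are pooled.** Take a 35/35 split overall, no marker–TBR relation within HIV status, and a marker D SD higher in HIV-infected people. The expected spurious difference is D × (HIV share of the elevated group − HIV share of the non-elevated group). False-positive rates come from simulating the pooled t-test.

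| Controls non-elevated | HIV shares (elevated; non-elevated) | Spurious difference, D = 0.5 to 1.0 | False-positive rate |
|---|---|---|---|
| 10 of 10 | 35/35; 25/35 | 0.14 to 0.29 SD | about 9% to 19% |
| 8 of 10 | 33/35; 27/35 | 0.09 to 0.17 SD | about 6% to 9% |
| 5 of 10 | 30/35; 30/35 | 0 | not above 5% |

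The same test confined to the HIV-infected participants stays at 5% in every row.

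**5. Steps 3 and 4 together.** With about 6 HIV-infected people at or below 1.8, pooling could make controls up to 10 of 16 in the non-elevated group.

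**The case against.** A reader might infer that the plan has put controls into this comparison and that HIV status therefore does confound it. The documents do not establish that. The sample-size text never says who the 70 are. Its opening sentence uses 70 for the HIV-infected group and calls the uninfected people controls, so the 70 may simply be the HIV-infected group. In that case nothing is pooled, the confounding argument falls away, and a denominator slip remains. The between-group paragraph also follows an analysis limited to HIV-infected patients, under an aim with the same limit. Subject Selection gives the controls a separate role: showing whether relationships are HIV-specific. Even under pooling, confounding needs both TBR (or plaque) status and the marker to differ by HIV status, and the documents do not quantify either difference for this sample. The group tests are additional to regression models that admit further confounders, and the detectable effect is expressly conditional on a 50% rate.

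These points stand, and they limit the claim to what can happen if controls are pooled. They do not rescue the 70: on the reading that avoids pooling, 10 of the 70 have no TBR. Nor does the regression settle the matter. Its named covariates omit HIV status, and the group tests are unadjusted whatever the regression does.

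**Conclusion.** The sizing statement needs correcting on either reading. For the question Aim 1 asks, the available number is at most 60, and d = 0.68 has 73.6% power at an even split rather than 80%. The plan's arithmetic for 35 versus 35 is correct; the population is not.

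Confounding by HIV status is a possibility that the plan leaves open. Its size rests on the assumed marker gap and control TBR status: from no inflation to a false-positive rate of about 19%, the upper end needing every control non-elevated and a 1.0 SD gap. The plaque comparison shares this exposure through the same unadjusted tests, but it is not sized, so no power figure for it is in error.

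The value 0.74 should not be read as the expected sensitivity either. Under normality and the plan's own TBR figures, the split would be far from even and detectable d about 1.23.

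This is a supplementary cross-sectional comparison, and the randomized primary analysis is unaffected. The change is still worth making, because it corrects a stated figure and removes a possible bias at almost no cost.

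**What to change.** - **Between-group comparisons:** state that both the plaque and the elevated-TBR contrasts are made within HIV-infected participants who have Part 2 imaging (n up to 60).
- **If controls are pooled as a secondary analysis:** say which ones, the 10 parent-study controls or also the 15 neurological-substudy controls, who have CTA and FDG-PET as well. Include HIV status through linear regression or a stratified rank test such as van Elteren's.
- **Aim 1A Sample Size Determination:** replace the 70-person figure with n = 60. Give detectable d of about 0.74 at 80% power if half are elevated (73.6% power at d = 0.68). Beside it, state that a TBR of 2.24 (SD 0.35) with the 1.8 cut implies, under normality, about 54 versus 6, with detectable d about 1.23 and about 34% power at d = 0.68.

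The cost is a few sentences and a less favourable stated detectable effect. No new data or patients are needed.

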Nutritional Status and Exercise Activity: Food records will be analyzed for protein, carbohydrate, and fats (Nutritional Data Systems, Minneapolis, MN). The Bouchard 3-Day Physical Activity Record will also be administered.

Transcriptomic profiling of circulating monocytes: RNA from sorted CD14+ monocytes from the blood will be converted into a cDNA library using Illumina TrueSeq RNA sample preparation kit followed by paired end 50 cycles sequencing by HiSeq. Data will be analyzed using TopHat and Cufflinks and visualized using CummRbund as described by Trapnell *et al*⁴⁹. These software tools will allow us to analyze the data sets for differences in transcriptional splice variants. For analysis, we will specifically examine differential expression of transcripts as well as perform pathway analysis using IPA Transcriptional Analysis (Ingenuity Systems).

Medical Record Review: Medical records will be reviewed for relevant clinical data for subjects who are currently followed at MGH or BWH for clinical care. Subjects who receive clinical care from external providers will be asked to sign a Release of Information form. We will request and/or review relevant medical history, laboratory results and treatment history for HIV and/or Hepatitis B and C.

Fecal Occult Blood Testing (FOBT) Using the Fecal Immunochemical Test (FIT): Participants in the Randomized Study of Teduglutide vs. Placebo will be given a FIT kit to perform the test at home 1 year after starting the study medication (6 months after the study is over) to screen for colorectal cancer. Participants will be asked to asked to collect a very small stool sample using a brush so that they do not directly handle the fecal material. Using the brush, subjects will place the sample on the collection card, place the card in an envelope provided and mail to the laboratory.

Functional Assessment:

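### Aim 1B tests 27,000 genes from one sorted cell type with no low-expression filter, and its stated 80% power does not reproduce with an ordinary two-sided t-test

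*Combined protocol and SAP*

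**What the plan says.** The sample size paragraph under RNA Sequencing Subset (Aim 1B) sets out the calculation "For *RNA-Seq* analysis using 7 patients with CVD and 7 without". It states that "there will be 27,000 genes to be included in the initial testing of which about 140 genes are expected" to differ, "with a two to three times of the standard deviation of the fold difference in the expression levels". It targets an FDR of 20% or less and claims at least 80% power to detect at least 112 genes "with an effect size of 2.7×SD with p<0.0011", which it calls "multiple testing adjusted alpha=0.0011".

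The analysis paragraph of the same section names LIMMA and adds that "Holm's and Benjamin-Hochberg methods will be applied for correcting multiple testing". The laboratory description (Transcriptomic profiling of circulating monocytes) says "RNA from sorted CD14+ monocytes from the blood will be converted into a cDNA library". It then goes from sequencing to differential expression and pathway analysis. Neither section describes dropping genes with few or no reads before testing.

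The Aim 1B section does not state sidedness. The Between group comparisons paragraph of the Aim 1A plan says that all tests are two-sided.

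**The concern.** A single sorted cell type does not express every gene. A gene with almost no reads across 14 libraries has practically no chance of showing a 2 to 3 SD difference between groups, yet it counts in the multiplicity correction like any other. With 7 per group the cut-off matters: each unneeded gene makes it stricter and costs some true genes. Aim 1B contrasts patients by coronary atherosclerosis and by microbial translocation, then compares the pathways that emerge, so losses in both gene lists feed into that comparison.

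There is also a separate question: whether the stated power follows from the stated inputs at all.

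**Working it through.** **Inputs from the Aim 1B sample size paragraph.** n = 7 per group; m = 27,000 genes; m1 = 140 true genes, so m0 = 26,860 null genes; effect d = 2.7 SD; alpha = 0.0011; FDR target 20%; 112/140 = 80%. Two-sided testing is taken from the Aim 1A plan.

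**Step 1: the plan's own figure.** For an ordinary two-sample t-test, df = 12 and the noncentrality is 2.7 × √(7/2) = 5.05. From the noncentral t at two-sided alpha 0.0011:
- power per gene = 74.8%
- expected true genes found = 140 × 0.748 ≈ 105, not 112.

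**Step 2: does alpha 0.0011 match the FDR target?** Expected false positives are 0.0011 × 26,860 = 29.5. With 112 true positives the FDR is 29.5/(29.5 + 112) = 20.9%, slightly above the target. The alpha that gives exactly 20% with 112 true positives is 28/26,860 = 0.00104, and power there is 74.0%.

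**Step 3: tie the cut-off to FDR 20%.** Solve alpha × m0 / (alpha × m0 + 140 × power(alpha)) = 0.20. At 27,000 genes alpha ≈ 0.00095, power = 72.6%, and about 102 of 140 genes are found. A simulation of Benjamini-Hochberg at 20% with independent genes gave 101.

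**Step 4: effect of testing fewer genes.** This solves the same equation, assuming all 140 true genes survive the filter. The documents give no expressed fraction, so the gene count is an assumption shown as a range.

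| Genes tested | Cut-off | Power at 2.7 SD | True genes found |
|---|---|---|---|
| 27,000 | 0.00095 | 72.6% | 102 |
| 20,000 | 0.0014 | 77.9% | 109 |
| 17,500 | 0.0016 | 80.0% | 112 |
| 16,000 | 0.0018 | 81.4% | 114 |
| 13,500 | 0.0022 | 83.8% | 117 |

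Reaching 80% this way means removing (27,000 − 17,500)/27,000 = 35% of the genes.

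**Step 5: sensitivity to the test.** With all 27,000 genes kept, a LIMMA-type moderated t (prior df added to the 12) gives:

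| Prior df | Power at alpha 0.0011 | Power tied to FDR 20% |
|---|---|---|
| 2 | 79.4% | 78.5% |
| 3 | 81.2% | 80.6% |
| 4 | 82.6% | 82.3% |

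Other readings at alpha 0.0011 are 83.8% for a one-sided t-test and 78.9% for seven matched pairs tested two-sided.

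**Step 6: lower end of the expected effect range.** At 2 SD, with the cut-off tied to FDR 20%, power is about 18% at 27,000 genes and about 35% at 13,500.

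**The case against.** The strongest reply is that the plan names LIMMA, not an ordinary t-test. Variance moderation alone reaches 80% on all 27,000 genes once the prior df is about 2.3 at alpha 0.0011, or about 2.7 when tied to FDR 20%. This stands. The prior df is estimated from data and is not in the documents, so neither adequacy nor shortfall is established for the moderated test.

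A reader might infer that the missing filter is what pulls power below 80%. The documents do not support that. At a fixed alpha of 0.0011 the ordinary t-test gives 74.8% however many genes are tested, so the mismatch with the stated figure lies in how that figure was calculated. The filter matters through the cut-off that the FDR target allows.

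A reader might also infer that a filter would restore 80%. That is conditional too. A filter that leaves 20,000 genes falls short under the ordinary t-test. Losing true genes erodes the gain: at 15,000 genes with 7 of the 140 removed, about 109 are found, still above 102 but below 112.

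Finally, 27,000 appears only as a planning number, and nothing in the analysis text forbids filtering. This is fair, and testing too many genes does not invalidate FDR control. But an unstated filter is one that can be chosen after results are seen. Because the profiling uses stored samples after the study is completed, the rule can be fixed beforehand.

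**Conclusion.** The point holds in two separate parts.

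First, no low-expression filter is described. Testing genes with almost no reads tightens the cut-off without benefit. Under an ordinary t-test at 2.7 SD with all true genes retained, cutting the tested set to between 20,000 and 13,500 would add about 7 to 15 true genes (from 102 to between 109 and 117). The size depends on an expressed fraction that the documents do not give.

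Second, the claimed power of at least 80% is not delivered by an ordinary two-sided two-sample t-test on the plan's inputs: it is 74.8% at alpha 0.0011 and 72.6% when tied to FDR 20%. A moderated t with prior df of about 3 or more would meet the claim, but the plan does not say that this was the calculation.

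A filter is worthwhile under either test; with prior df 2, for example, going from 27,000 to 20,000 genes raises power from 78.5% to 82.7%. It does not rescue effects at the 2 SD end of the plan's range. This is an efficiency and reporting weakness in a mechanistic subset. It does not touch error control or the randomized comparison.

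**What to change.** - Before LIMMA, remove genes with low overall counts by a rule fixed in advance and computed without group labels, for example a minimum read count in at least 7 of the 14 libraries.
- Use one filtered gene set for both 7 versus 7 contrasts, so that their pathways are compared on the same genes. Apply the same rule to the before/after contrast in seven teduglutide patients.
- Apply Benjamini-Hochberg at 20% to the remaining genes and name it as the governing method. At Holm's first step (0.05/27,000) ordinary t power is only about 4% per gene at 2.7 SD.
- Restate the power with the test named (ordinary or moderated t, two-sided, with any assumed prior df), a cut-off consistent with FDR 20%, and the filtered gene count shown as a range.

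The cost is a few sentences of plan text and a line of code, with no extra samples or sequencing. The downside is that genes below the count limit go untested, and any true gene among them is lost.

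### Aim 1B RNA-Seq: the stated power (at least 80%) and FDR (20% or less) for 7 vs 7 need an unstated one-sided test or LIMMA prior; a two-sided ordinary t-test gives about 75% and 22%

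*Combined protocol and SAP*

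**What the plan says.** The Sample Size Determination text under RNA Sequencing Subset (Aim 1B) plans "7 patients with CVD and 7 without" and says "there will be 27,000 genes to be included in the initial testing". Of these, "about 140 genes are expected to be differentially expressed significantly with a two to three times of the standard deviation" of the fold difference. "With a targeted false discovery rate (FDR) of 20% or less", it gives "the power to detect at least 112 differentially expressed genes significantly with an effect size of" 2.7 SD, at a per-gene alpha of 0.0011, as at least 80%.

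The analysis text just before it names LIMMA as the test and adds that "Holm's and Benjamin-Hochberg methods will be applied for correcting multiple testing". It does not say which of the two decides significance. Neither text gives the sidedness, the power formula, or a prior degrees of freedom for LIMMA.

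The nearest rule on sidedness, "All tests will be 2-sided", closes the Between group comparisons paragraph for Aim 1A. The plan's two other t-test power statements (the elevated-TBR comparison and the Aim 2 TBR change) each specify a two-sided test. The Research Design section adds that the RNA-Seq groups are matched on age and traditional cardiovascular risk factors.

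**The concern.** This paragraph is the only quantitative support for 7 patients per group in Aim 1B. A reader who applies the plan's two-sided convention and a standard two-sample t-test does not recover 80% power or a 20% FDR. Aim 1B looks for signatures without naming a direction, so two-sided is the natural reading.

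The count of 112 is also presented as a threshold that will be met with at least 80% probability, although it equals 80% of 140. At stake is how many true genes, and what share of false ones, the investigators should expect in the resulting gene list.

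**Working it through.** **Inputs (all from the Aim 1B sample size text).** n = 7 per group; effect d = 2.7 SD; alpha = 0.0011; 27,000 genes, of which 140 truly differ, so 27,000 − 140 = 26,860 are null; FDR target 20%; target count 112 = 0.80 × 140.

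**Formulas.** Per-gene power comes from the noncentral t with df = 2×7 − 2 = 12 and noncentrality 2.7 × √(7/2) = 5.05. Expected false positives = 26,860 × 0.0011 = 29.5. FDR is approximated by 29.5 / (29.5 + true positives), with true positives = 140 × power. The probability of at least 112 detections is a binomial tail with 140 trials, which assumes independent genes.

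**1. Reproducing the plan's figure.** A one-sided exact t-test comes close:
- Power is 83.8%, so expected true positives are 140 × 0.838 = 117.4.
- FDR = 29.5 / (29.5 + 117.4) = 20.1%.
- P(at least 112) = 0.91.
- The one-sided alpha that gives exactly 20% FDR is 0.00109, which rounds to the plan's 0.0011.

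**2. Two-sided ordinary t-test.**
- Power is 74.8%, so expected true positives are 104.7.
- FDR = 29.5 / (29.5 + 104.7) = 22.0%.
- P(at least 112) = 0.09.
- Power of 80% needs d = 2.82. With 8 per group, power at 2.7 SD would be 86.3%.

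**3. Two-sided moderated t-test (LIMMA), df = 12 + prior df.** The prior df is an assumption in every row.

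| Prior df | Power per gene | FDR | P(at least 112) |
|---|---|---|---|
| 0 | 74.8% | 22.0% | 0.09 |
| 2 | 79.4% | 21.0% | 0.48 |
| 3 | 81.2% | 20.6% | 0.68 |
| 4 | 82.6% | 20.4% | 0.82 |
| 6 | 84.9% | 19.9% | 0.95 |

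So about 3 prior df are needed for 80% per gene, about 4 for an 80% chance of at least 112 genes, and about 6 for FDR 20%.

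**4. Alpha against FDR, whatever the sidedness.** With 112 true detections, FDR = 29.5 / (29.5 + 112) = 20.9%. Holding 20% with 112 true detections allows 112 × 0.2/0.8 = 28 false positives, so alpha = 28/26,860 = 0.00104. For a two-sided ordinary t-test at 2.7 SD, 112 is not the expected count; solving alpha and power together gives alpha of about 0.00095 and power of about 73%.

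**5. What 112 means.** At exactly 80% per-gene power the expected count is 0.80 × 140 = 112, and P(at least 112) is about 0.55.

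**6. The stated effect range.** At alpha 0.0011:

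| Effect | Two-sided | One-sided |
|---|---|---|
| 2 SD | 37% | 49% |
| 2.5 SD | 65% | 76% |
| 2.7 SD | 75% | 84% |
| 3 SD | 86% | 92% |

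If the 140 effects were spread uniformly over 2 to 3 SD (an assumption), average two-sided power would be about 64%, or about 90 genes, with FDR about 25%. The one-sided average would be about 74%.

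**The case against.** The strongest reply is that the paragraph is coherent as written. A one-sided calculation brings power, alpha, FDR and the count of 112 together almost to rounding, which suggests an unstated convention and not a slip. The two-sided sentence belongs to Aim 1A and is joined to a 0.05 threshold that cannot govern Aim 1B. The planned test is LIMMA, which borrows variance across genes and so has more than 12 df; taking zero prior df is the least favourable case. The groups are matched, and a paired two-sided t-test with 7 pairs gives 78.9% if 2.7 is in units of the SD of the paired difference.

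Much of this stands. A reader might infer that the power figure is simply wrong, or that 7 per group has been shown to fall short. The documents support neither: the figure can be recovered, and the prior df is unknown. What does not stand is the idea that the text needs no change. A one-sided test departs from the only sidedness the plan states and does not suit a search in both directions, and relying on LIMMA requires a prior df that the plan omits. The 20.9% FDR at 112 detections remains on every reading, although it is under one point above target and starts from an approximate 140 genes.

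A reader might also infer from the mention of Holm that almost nothing would be found. At Holm's first step (0.05/27,000), two-sided power at 2.7 SD is indeed about 4%. But the power statement is tied to FDR and claims nothing under Holm, so this shows only that the declaration rule should be named. Quoting power at 2.7 SD is legitimate, since it lies inside the stated range; the 64% average depends on the assumed uniform spread.

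**Conclusion.** The point holds in a limited form. Under the plan's two-sided convention and an ordinary t-test, 7 vs 7 at 2.7 SD and alpha 0.0011 gives about 75% power per gene and about 105 of 140 genes, about 7 fewer than stated, with FDR about 22%. The stated figures need an assumption that the plan does not give. Extending the Aim 1A sidedness rule to Aim 1B is an inference, supported by the plan's other t-test power statements. The probabilities for the count assume independent genes.

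Two wording faults do not depend on sidedness: alpha 0.0011 with 112 true detections slightly exceeds the 20% FDR, and 112 is described as a count reached with at least 80% probability when it is the expected count at 80% per-gene power. Under the one-sided reading the probability claim happens to be true (0.91), but only because per-gene power is then above 80%.

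Severity is minor. Aim 1B is a discovery subset analysed on stored samples, and the randomized primary outcome is untouched.

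**What to change.** In the Aim 1B analysis and sample size text:

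- State the test, its sidedness and the power formula, including whether the SD is per group or of a matched difference.
- Restate power for a two-sided test at 7 vs 7: about 75% per gene at 2.7 SD with an ordinary t-test, 80% at about 2.82 SD. If LIMMA moderation is relied on, give the assumed prior df, its source and the resulting power instead.
- Set an alpha consistent with FDR 20%: about 0.00104 if 112 true detections are expected, or about 0.00095 (power about 73%) for the two-sided ordinary t-test at 2.7 SD.
- Replace the claim about reaching at least 112 genes with an expected number detected.
- Show power across 2 to 3 SD, labelling any average as resting on an assumed spread of effects.
- Name Benjamini-Hochberg at FDR 20% as the declaration rule, with Holm as supplementary only.

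The cost is wording only. The stated power becomes slightly less favourable; sample size and procedures do not change.
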